9.4 Statistical Analyses

9.4.1 General Considerations

All individual data will be listed as measured. All statistical summaries and analyses will be performed using SAS software (SAS Institute Inc, Cary, North Carolina, USA).

Continuous data will be summarized using an 8-point descriptive summary (n, mean, SD, median, IQR [25% quartile, 75% quartile], minimum, and maximum) or 7-point descriptive summary (n, mean, SD, CV, median, minimum, and maximum) unless otherwise specified.

Categorical data will be summarized using the frequency of events and percentage of total events.

Baseline definitions for each endpoint will be defined in the SAP.

Data will be presented by treatment group. Changes in primary, secondary, and exploratory endpoints will be analyzed over time, with change from baseline summarized for each post-baseline time point measured.

All efficacy analyses will be conducted on the ITT Population using a 2-sided alpha of 0.05. The primary endpoint and secondary endpoints will be reported using a multiplicity algorithm.

Efficacy analyses at Week 18 (primary and secondary) will compare tildacerfont treatment groups to placebo. Efficacy analyses at Week 76 will evaluate change from baseline only.

For missing data, a retrieved dropout approach will be used in which missing endpoint data for subjects who discontinued early will be imputed using data collected from subjects after discontinuation of study drug.

Any changes to the protocol-specified analyses will be pre-specified in the SAP prior to database lock.

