9.4.4 Analysis of the Exploratory Efficacy Endpoints

9.4.4.1 Testicular Adrenal Rest Tumor Endpoints

The exploratory endpoint, change in TART lesion volume at Week 18, will be analyzed using an ANCOVA model with baseline lesion size as a covariate and fixed effects for randomization strata and treatment. Additional covariates may be specified in the SAP.

The exploratory endpoint, change in TART lesion volume at Week 76, will be analyzed using a repeated measure mixed effects model with treatment and visit as fixed effects, subject as a random effect, and the baseline score as a covariate. Additional covariates may be specified in the SAP.

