9.4.4.4 Patient- and Clinician-Reported Outcomes Endpoints

Changes in SF-36 total score, IGA acne score, and mFG hirsutism score will be analyzed using a repeated measure mixed effects model with treatment (two covariates: randomized and group at Week 76) and visit as fixed effects, subject as a random effect, and the baseline score as a covariate if >2 timepoints are assessed. If only the baseline timepoint and a single post-baseline timepoint are assessed for the endpoint, an ANCOVA model with the baseline score as a covariate will be used with only a single treatment covariate (randomized treatment). There will be no imputation of missing data.

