9.4.4.5 Glucocorticoid Dose Reduction Endpoints

The proportion of subjects with at least a 5 mg/day HCe reduction from baseline in GC dose and A4 \leq ULN at Week 76 will be summarized using an exact score test through logistic regression using the randomization strata and treatment group at Week 76 in the model specification. Missing values for proportion endpoints will not be imputed and will be assumed to be failures. Additional covariates may be specified in the SAP.

Additional GC-related proportions, eg, proportion of subjects at specific dose levels, may be specific in the SAP.

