Clinical visits during Parts A, B, and C in the Treatment Period, the Open-Label Extension Period, and Follow-up Period will include efficacy, biomarkers, safety, and pharmacokinetic (PK) assessments. [Figure 1](#) depicts study visits from Screening Period to Follow-up Period and [Figure 2](#) depicts study visits during the optional Open-Label Extension Period.

The maximum duration per subject of the main Treatment Period of Study SPR001-203 is expected to be up to 87 weeks (i.e., a maximum of 45-day Screening Period, a 6-week Run-in Period, a 70-week Treatment Period, and a 30-day safety Follow-up Period). Including the optional Open-Label Extension Period (240 weeks), the maximum duration per subject is expected to be up to 327 weeks. Subjects randomized to tildacerfont in Part A will receive up to 70 weeks of treatment with tildacerfont in the main study. For subjects randomized to placebo in Part A, this will include up to 58 weeks of treatment with tildacerfont in the main study. Assessments and procedures for evaluation of safety, efficacy, PK, and biomarkers will be conducted per the protocol-specified schedule (see Appendix A: [Table 13](#), [Table 14](#), and [Table 15](#)).

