### **13.5.7 Change from Baseline Analyses through Week 76**

Exploratory Efficacy Analyses 3.7 to 3.11 in [Table 1](#) are the change from baseline at study Week 76 in patient- and clinician-reported outcomes (SF-36 [3.7], IGA acne score [3.8], mFG hirsutism score [3.9]); Exploratory Efficacy Analysis 3.10 is the percent of subjects with at least a 5 mg/day (HCE) reduction from baseline to study Week 76 in GC dose; and Exploratory Efficacy Analysis 3.11 is the change from baseline at study Week 76 in lesion volume of TART(s). For each of these study Week 76 exploratory endpoints, the efficacy of tildacerfont is evaluated by comparing the study Week 76 assessment against baseline.

For Exploratory Efficacy Analyses 3.7 and 3.11, an ANCOVA model will be applied, and results described, in the same manner as that for Exploratory Efficacy Analysis 3.6.

For Exploratory Efficacy Analysis 3.10, logistic regression modelling via SAS PROC GENMOD will be applied in a similar manner as for Exploratory Efficacy Analysis 3.1. The logistic regression model will include CG response (= 0 or 1) as the dependent variable; treatment group (0 = placebo, 50 = 50 mg QD tildacerfont, 100 = 100 mg QD tildacerfont, and 200 = 200 mg QD tildacerfont) and sex (0=male, 1=female as categorical covariates; log baseline A4 and baseline

GC dose (in HCe) as continuous covariates. The model will use a binomial distribution with the logit link function and a significance level of 0.05 2-sided.

The odds ratio for GC response at study Week 76 to each tildacerfont dose level versus placebo group, together with the associated 95% CI and 2-sided p-value will be extracted from the model. SAS code will be of the form,

```
PROC GENMOD DATA=x;
  CLASS SUBJECT TREATMENT VISIT;
  MODEL RESPONSE = TREATMENT VISIT / DIST=BINOMIAL LINK=LOGIT TYPE3
    AGGREGATE=TREATMENT;
  LSMESTIMATE TREATMENT 'OR 50MG V PCBO' -1 1 0 0 / EXP CL ALPHA=0.05;
  LSMESTIMATE TREATMENT 'OR 100MG V PCBO' -1 0 1 0 / EXP CL ALPHA=0.05;
  LSMESTIMATE TREATMENT 'OR 200MG V PCBO' -1 0 0 1 / EXP CL ALPHA=0.05;
  RUN;
```

Since Exploratory Efficacy Analyses 3.8 and 3.9 relate to ordinal, logistic regression modelling via SAS PROC GENMOD will be applied as described in [Section 13.5.1.2](#).

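### SAP 13.5.7 judges the Week 76 endpoints against baseline but writes out contrasts with a placebo group that no longer exists, and gives no pooled estimate with a confidence interval

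*SAP*

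**What the plan says.** SAP 13.5.7 covers SF-36 (3.7), acne (3.8), hirsutism (3.9), the GC-reduction response (3.10) and TART volume (3.11). It opens by stating that for each of them "the efficacy of tildacerfont is evaluated by comparing the study Week 76 assessment against baseline". Protocol 9.4.1 takes the same line: "Efficacy analyses at Week 76 will evaluate change from baseline only".

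For 3.10 the section then fits a logistic model with treatment coded 0, 50, 100 and 200, and extracts "The odds ratio for GC response at study Week 76 to each tildacerfont dose level versus placebo group", with a 95% CI and p-value. The three estimate statements in the example code are the same three dose-against-placebo contrasts.

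SAP Section 5 says what the placebo-randomised arm has received by then: "For subjects randomized to placebo in Part A, this will include up to 58 weeks of treatment with tildacerfont in the main study". SAP 5.2.1 and Protocol 6.1.2 plan 200 mg for every subject from Week 30.

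The protocol's endpoint sections use several treatment terms at Week 76:
- 9.4.4.4, repeated-measures branch: "treatment (two covariates: randomized and group at Week 76) and visit as fixed effects". Its ANCOVA branch uses randomised treatment alone.
- 9.4.4.1, TART volume: "will be analyzed using a repeated measure mixed effects model with treatment and visit as fixed effects".
- 9.4.4.5, GC reduction: "using the randomization strata and treatment group at Week 76 in the model specification".

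**The concern.** The stated question and the written inference differ. The question is how subjects at Week 76 compare with their own baseline. The inference for 3.10 compares randomised arms, all of them on active drug and planned on the same dose. If tildacerfont worked equally well in every sequence, the expected odds ratio would be 1. A reader who sees a null odds ratio labelled as dose against placebo could take it to mean that the drug does not allow GC reduction. The same label carries over to quality of life, acne, hirsutism and TART volume.

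SAP Table 1 words 3.7, 3.8, 3.9 and 3.11 as being across all relevant ITT subjects, yet 13.5.7 writes out no pooled estimate with a CI for any of the five analyses.

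**Working it through.** **1. Time on drug by Week 76.** Inputs are the visit schedule and dosing rules (Protocol 6.1.2, SAP 5.2.1): randomised dosing from Week 6, Part B from Week 18, possible escalation after Weeks 18 and 24, and 200 mg for all from Week 30. Switches are taken at the visit.

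| Randomised arm | Weeks on tildacerfont | Weeks at 200 mg |
|---|---|---|
| Placebo | 76 − 18 = 58 | 76 − 30 = 46 to 76 − 24 = 52 |
| 50 mg | 76 − 6 = 70 | 46 to 52 |
| 100 mg | 70 | 46 to 76 − 18 = 58 |
| 200 mg | 70 | 70 |

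The 58 and 70 reproduce SAP Section 5. Protocol 6.1.2 allows a supply delay after Weeks 18 and 24 without giving its length. An assumed 1 to 2 weeks turns 58 into 56–57 and 52 into 50–51. The 46 does not change, because no A4 result is needed at Week 30 (Protocol 1.3.3, footnote 20).

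The placebo and 50 mg arms have the same planned range at 200 mg. At the roughly 60-hour single-dose half-life in Protocol 4.3, 46 weeks is 46 × 7 × 24 / 60 = 128.8 half-lives, so planned steady-state exposure at Week 76 is the same in every arm. The arms differ in start time and in dose path through Part B.

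**2. What each analysis yields, following the cross-references.**

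| Analysis | Arm contrast | Change-from-baseline output |
|---|---|---|
| 3.7, 3.11 | Dose-minus-placebo LS-mean differences, from 3.6 (13.5.6.2) | By-arm LS means with CIs |
| 3.8, 3.9 | Odds ratios against placebo, from 13.5.1.2, whose own wording is Week 18 | None written out in 13.5.7 |
| 3.10 | Odds ratios against placebo, written out | By-arm proportions, if carried over from 13.5.1; that template has no CI and no pooled row |

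**3. Precision.** The sample size gives 15/(1 − 0.15) = 17.6, so 18 per arm and 72 in total, which reproduces the SAP. The documents give no response rate for 3.10, so 10% to 50% is assumed, with one true rate in all arms.

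Unadjusted odds-ratio 95% CI around 1: exp(±1.96 × √(2/(18p(1 − p)))). Pooled proportion: Clopper-Pearson, n = 72.

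| Assumed rate | Odds-ratio CI, 18 v 18 | Pooled count | Exact 95% CI |
|---|---|---|---|
| 10% | 0.11 to 8.8 | 7/72 | 4.0% to 19.0% |
| 30% | 0.24 to 4.2 | 22/72 | 20.2% to 42.5% |
| 50% | 0.27 to 3.7 | 36/72 | 38.0% to 62.0% |

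For 3.7, 95% CI half-widths in SD units:
- Two-arm difference: t(34) × √(2/18) = 0.68, or t(28) × √(2/15) = 0.75 with 15 per arm.
- Pooled mean change: t(71)/√72 = 0.23, or t(60)/√61 = 0.26 after 15% dropout (72 × 0.85 ≈ 61).

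These columns estimate different quantities. They show how little a null arm contrast would exclude, not a gain in efficiency.

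**The case against.** The coding 0/50/100/200 can only mean the randomised arms, and SAP Sections 5 and 5.2.1 say plainly that everyone moves to 200 mg. On that view the label is shorthand that a footnote would cure. Comparing randomised arms is also the only randomised comparison left at Week 76, whereas a pooled estimate is uncontrolled. The across-all wording in Table 1 may name the population rather than require a pooled estimator, and Table 1 does not use it for 3.10. SAP Section 4 says the SAP governs where it is inconsistent with the protocol. The endpoints are exploratory and outside alpha control (SAP 10.5).

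Most of this stands as a limit on impact. The contrasts are valid randomised comparisons if named for what they are. But the rule that the SAP governs cannot settle a mismatch inside the SAP's own section, and a footnote would not supply the estimate that the section says it wants.

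A reader might also infer that the plan has no comparison with baseline at all. The documents do not support that. The 3.10 response in Table 5 already contains the reduction from baseline. By-arm LS means with CIs exist for 3.7 and 3.11, and by-arm proportions may carry over to 3.10. The actual-dose default in SAP Section 9 may also produce a single 200 mg descriptive column. Nor is Section 15 silent throughout: it records the move to a cumulative logit model for acne and hirsutism. What it does not record is the Week 76 comparator or treatment term.

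**Conclusion.** The point holds for labelling and for a missing estimate. Followed as written, 13.5.7 reports each dose against a placebo group that has been on tildacerfont for up to 58 weeks, and it specifies no pooled Week 76 estimate with a CI for any of 3.7 to 3.11. With about 18 per arm, the 3.10 odds ratio would be compatible with roughly a four-fold difference in either direction at an assumed 30% response, so a null result would say little.

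The exposure figures rest on planned dosing and visit-day switches; the precision figures rest on assumed response rates and unadjusted formulas. The likely harm is misreading of exploratory results. Nothing here touches the primary or secondary conclusions. The change should be made before the final analysis.

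**What to change.** In SAP 13.5.7, specify a pooled Week 76 estimate with a 95% CI over the relevant ITT subjects:
- **3.7 and 3.11:** mean change from baseline on the untransformed scale. If clearly non-normal, use the median change with a CI or a signed-rank method. Do not pool the ranks defined in 13.5.6.1: all non-missing changes are ranked together, so their mean is always (n + 1)/2.
- **3.8 and 3.9:** proportions improved, unchanged and worsened, the categories 13.5.7 already names.
- **3.10:** proportion meeting Table 5 in full (reduction of at least 5 mg/day HCe and A4 ≤ ULN, missing counted as failure), with an exact CI. The prose in 13.5.7 omits the A4 component.

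State that the pooled estimates are uncontrolled and cannot separate drug effect from time or regression to the mean. Keep the arm contrasts as supportive, labelled *randomised-sequence comparison (earlier versus delayed start and Part B dose path)*. Add a Section 15 entry recording the Week 76 comparator and treatment term relative to Protocol 9.4.1, 9.4.4.1, 9.4.4.4 (both branches) and 9.4.4.5.

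The cost is SAP wording, one log entry and minor programming, with no new data. The arm contrasts will remain imprecise.

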### 9.3.16 Responder Definitions

The exploratory variables are proportions of responders based on each of the serum hormone assessments and GC. Indicator variables will be created for each of the three responder criteria as depicted in [Table 5](#). Missing assessments are counted as non-responders.

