#### 13.5.1.2 Statistical Modeling and Testing

A generalized estimating equations (GEE) model via SAS PROC GENMOD will be used to evaluate A4 response (defined as  $A4 \leq 1x, 1.25x, 1.5x, 1.75x$  and  $2x ULN$ , with a separate

analysis for each ULN cutoff). The model will include response (= 0 or 1) as the dependent variable; treatment group (0 = placebo, 50 = 50 mg QD tildacerfont, 100 = 100 mg QD tildacerfont, and 200 = 200 mg QD tildacerfont), time (=study week 10, 14 and 18), sex (0=male, 1=female), and the interaction of treatment and time as categorical covariates; log baseline A4 and baseline GC dose (in HCe) as continuous covariates. The link function will be logit and distribution will be binomial. Subject IDs are used to identify the repeated measures of visits within subjects with an exchangeable working correlation structure. If the model fails to converge, the following working correlation structures will be tried in order until convergence is reached: unstructured, independent and AR(1). The model will use a binomial distribution with the logit link function and a significance level of 0.05 2-sided.

The odds ratio for response at study Week 18 for each tildacerfont dose level versus placebo group, together with the associated 95% CI and 2-sided p-value will be extracted from the model. The same will also be extracted for the odds ratio of response at study Weeks 10 and 14. SAS code will be of the form,

```
PROC GENMOD DATA=x;
  CLASS SUBJECT TREATMENT VISIT;
  MODEL RESPONSE = TREATMENT VISIT TREATMENT*VISIT / DIST=MULTINOMIAL
    LINK=LOGIT TYPE3 AGGREGATE=TREATMENT;
  REPEATED SUBJECT=PATIENT/TYPE=IND;
  LSMESTIMATE TREATMENT 'OR 50MG V PCBO' -1 1 0 0 / EXP CL ALPHA=0.05;
  LSMESTIMATE TREATMENT 'OR 100MG V PCBO' -1 0 1 0 / EXP CL ALPHA=0.05;
  LSMESTIMATE TREATMENT 'OR 200MG V PCBO' -1 0 0 1 / EXP CL ALPHA=0.05;
RUN;
```

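### SAP 13.5.7: the code template for the glucocorticoid-reduction endpoint (3.10) does not fit the model described in the text, and by default its odds ratios are for non-response

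*SAP*

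**What the plan says.** SAP Table 1 defines analysis 3.10 as the proportion of subjects who, at Week 76, have cut their GC dose by at least 5 mg/day in hydrocortisone equivalents and have A4 at or below the ULN. SAP Table 5 codes this as 1 when met and 0 when not met or missing; section 9.3.16 adds "Missing assessments are counted as non-responders".

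SAP 13.5.7 then describes the model: "The logistic regression model will include CG response (= 0 or 1) as the dependent variable". The explanatory variables are treatment group, sex, log baseline A4 and baseline GC dose. The quantity to report is "The odds ratio for GC response at study Week 76 to each tildacerfont dose level versus placebo group", with a 95% CI and a two-sided p-value.

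The code is introduced by "SAS code will be of the form". Its first two statements are "CLASS SUBJECT TREATMENT VISIT" and "MODEL RESPONSE = TREATMENT VISIT / DIST=BINOMIAL LINK=LOGIT TYPE3". Three LSMESTIMATE lines follow, each contrasting one dose with placebo and exponentiating the result. There is no REPEATED statement and no EVENT= or DESCENDING option.

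Section 13.5.7 says 3.10 is handled similarly to 3.1. The 3.1 template in 13.5.1.2 is a multi-visit model and contains "REPEATED SUBJECT=PATIENT/TYPE=IND".

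**The concern.** Text and code in the same section specify different models. A programmer who follows the code would produce an estimate that is not adjusted as the text requires and that points the opposite way from its label.

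The labels would not reveal this. A line headed `OR 200MG V PCBO` with a value below 1 reads as fewer responders on that arm, when under the default it would mean more. Endpoint 3.10 is the only GC-dose endpoint among the main-study analyses in SAP Table 1, so a misread direction would affect the study's one modelled result on GC sparing.

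**Working it through.** The documents give no effect size, power or expected response rate for 3.10, so there is no planned figure to reproduce. The check sets text against template and then shows the size of the direction error.

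**1. Text against template (both SAP 13.5.7)**

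| Element | Text | Template |
|---|---|---|
| Time point | Week 76 | Not stated; VISIT is in CLASS and MODEL |
| Treatment | Yes | Yes |
| Sex | Yes | Absent |
| Log baseline A4 | Yes | Absent |
| Baseline GC dose | Yes | Absent |
| Visit effect | Not named | Present |
| Subject | One outcome each | In CLASS, never used |
| Event modelled | Response | Not specified |

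**2. Direction**

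Input from the SAP: 1 = responder, 0 = non-responder or missing (Table 5). Input from outside the SAP: PROC GENMOD's standard default, which models the lower-ordered response level, here 0.

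Since logit P(Y=0) = −logit P(Y=1), every treatment contrast changes sign. Exponentiating gives the reciprocal, and the Wald statistic keeps its absolute value.

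- Assumed response 40% versus 15%: odds ratio for response = (0.40/0.60)/(0.15/0.85) = 3.78. Template: 1/3.78 = 0.26.
- Assumed 8 of 18 versus 3 of 18 (18 per arm is the SAP section 7 target), unadjusted: odds ratio for response = (8/10)/(3/15) = 4.00, 95% CI 0.85 to 18.84, p = 0.080. Template: 0.25, 95% CI 0.053 to 1.18, p = 0.080.

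The reciprocal holds whichever rows are supplied.

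The same default points the other way in the ordinal template of 13.5.1.4. There the best category, A, sorts first, so a benefit appears as an odds ratio above 1. A reader who learns the direction from that table would misread 3.10.

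**3. Which rows are supplied**

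The SAP does not say whether data set `x` holds one row per subject or several.

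- *Week 76 only, as endpoint and text imply.* VISIT has one level and is redundant with the intercept. The design effect is 1 + (1 − 1)ρ = 1, so there is no inflation; a simulation with 18 per arm and a 25% response rate in every arm rejected in 3% of runs.
- *Several visits stacked, which the SAP does not describe.* Without REPEATED, a subject's correlated responses are treated as independent, and the treatment contrast averages over visits instead of estimating Week 76. Protocol 6.5.1.4 starts GC reduction only after the Week 38 result, so at most four visits could carry responses (Weeks 46, 58, 70 and 76). With design effect 1 + 3ρ and type I error 2{1 − Φ(1.96/√DE)}: ρ = 0.3 gives DE 1.9 and 0.155; ρ = 0.5 gives 2.5 and 0.215; ρ = 0.8 gives 3.4 and 0.288. Here ρ is assumed and response rates are taken as constant over visits, which is unlikely during a taper. These figures illustrate the risk and do not forecast it.

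**4. What the arms mean at Week 76**

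SAP 5.2.1 puts every subject on 200 mg from Week 30, including those randomised to placebo. The contrasts therefore compare former randomised arms. The 40% versus 15% example shows the arithmetic of inversion and is not an expected drug-placebo difference.

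**The case against.** The strongest reply is that this is a sketch. The SAP presents the code only as a form, and the full model stands directly above it. Other templates are abbreviated in the same way: those in 13.5.1.2 and 13.5.1.4 also omit sex, log baseline A4 and baseline GC dose, and the one in 13.5.1.2 shows a multinomial distribution and independence working correlation where its text says binomial and exchangeable. The inversion rests on a software default that the SAP does not mention, GENMOD's output states which level it models, and the p-value is unaffected. SAP 10.5 gives exploratory endpoints no alpha control.

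All of this stands, and it limits the severity. It does not remove the contradiction. The SAP does not say that text prevails over code. Section 4 makes the SAP govern over the protocol, so the exact score test with randomisation strata in protocol 9.4.4.5 is not a fallback. The abbreviated 3.1 template is a reason to correct both, since it has the same 0/1 coding and the same missing response level.

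A reader might also infer from the VISIT term and the absent REPEATED statement that repeated visits will be counted as independent subjects. The documents do not support this. Endpoint and text give one outcome per subject at Week 76, for which REPEATED is not needed, and VISIT looks like a leftover from the 3.1 code. Nor do they support stacking all five Part C visits at one common response rate. GC is held stable through Part B and the first reduction follows the Week 38 result, so a reduction is not expected at the Week 38 visit itself.

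**Conclusion.** The template does not implement the analysis that its own section specifies. Run as written, it gives an estimate without the three stated covariates and, under GENMOD's default, an odds ratio that is the exact reciprocal of the one named (3.78 becomes 0.26 in the assumed example). The p-value is not changed by the inversion. The effect of omitting the covariates cannot be sized from the documents.

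Standard errors that are too small, and a treatment effect averaged over visits, arise only if more than one visit per subject is supplied.

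The conclusion rests on Table 5's coding, on GENMOD's default, and on the template being used without a response option. Severity is minor: the endpoint is exploratory and no primary, secondary or safety conclusion depends on it.

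**What to change.** In SAP 13.5.7, replace the 3.10 template:

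- Restrict the data to the Week 76 analysis visit, one row per subject.
- Remove VISIT and the unused SUBJECT; use `CLASS TREATMENT SEX`.
- Fit `MODEL RESPONSE(EVENT='1') = TREATMENT SEX LBASEA4 BASEGC / DIST=BINOMIAL LINK=LOGIT`, where LBASEA4 is log baseline A4 and BASEGC is baseline GC dose.
- Label the contrasts as original randomised arm versus original placebo arm, with a note that all subjects are on 200 mg from Week 30.

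Set the event level in the same way in the binary template for 3.1 (13.5.1.2), with the binomial distribution that its text already states.

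If a supportive multi-visit model for 3.10 is wanted, specify it separately with a REPEATED statement on subject and a TREATMENT*VISIT term, and take the Week 76 contrast from it.

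The cost is a few lines of SAP code, with no change to data collection or design.

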#### **9.3.19 Modified Ferriman-Gallwey Total Score**

The mFG scores each of 9 body areas on a scale of 0 (no hair) to 4 (hairiness typical of a man), with the sum of the separate scores providing a hormonal hirsutism score.

The total score is the sum of the individual item scores and ranges from 0 to 36, with higher scores corresponding to body hair patterns more typical of a man.

A subject with hirsutism at baseline is defined as an mFG score of 8 or more.

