Since the change from baseline in IGA or mFG may have sparse values may have sparse values (i.e., < 5 distinctive values with counts  $\geq 5$ ), the change from baseline values will be further classified in fewer ordered categories (i.e., improvement, no change, worsening) prior to analysis.

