Protocol Section 9.4.4.1 specified the analysis of changes IGA acne score, and mFG hirsutism score using a repeated measure mixed effects model if >2 time points are assessed or an ANCOVA for a single post-baseline time point. Given that these scores are ordinal and not continuous variables, the cumulative logit model was deemed more appropriate for the analyses of these two exploratory endpoints.

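### SAP 13.5.7 sends the Week 76 acne and hirsutism analyses to a binary A4 model, leaves out each scale's baseline score, and in practice would reduce hirsutism change to its direction

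*SAP*

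**What the plan says.** **Model reference.** SAP 13.5.7 states that analyses "3.8 and 3.9 relate to ordinal, logistic regression modelling via SAS PROC GENMOD will be applied as described in" Section 13.5.1.2. That section is a GEE model for A4 response coded 0 or 1. Its terms are treatment, time (Weeks 10, 14 and 18), sex and treatment by time, with "log baseline A4 and baseline GC dose (in HCe) as continuous covariates".

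**Collapse rule.** The last paragraph of 13.5.7 begins "Since the change from baseline in IGA or mFG may have sparse values", defines sparse as "< 5 distinctive values with counts" of at least 5, and concludes that "the change from baseline values will be further classified in fewer ordered categories (i.e., improvement, no change, worsening) prior to analysis".

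**Scale and population.** For mFG, SAP 9.3.19 says "The total score is the sum of the individual item scores and ranges from 0 to 36" and defines hirsutism at baseline as a score of 8 or more. Analysis 3.9 is limited to female subjects meeting that definition. SAP 5.2.5.4 places both scales at Weeks 6, 18 and 76.

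**Declared change.** Section 15 says the two scores are ordinal and that "the cumulative logit model was deemed more appropriate for the analyses of these two exploratory endpoints". The cumulative logit that the SAP writes out is in 13.5.1.4, again with log baseline A4 and baseline GC dose as its continuous covariates.

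**Protocol.** Section 9.4.4.4 specifies a mixed model with treatment and visit, "subject as a random effect, and the baseline score as a covariate". Its fallback, an ANCOVA for a single post-baseline timepoint, also adjusts for the baseline score.

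**The concern.** Three things do not fit together. The referenced model cannot take the outcome that the same section defines. The one covariate most directly tied to change on each scale is missing, and a hormone covariate stands in its place. And a sum score with many levels would be cut to three categories at the sample sizes this trial can produce.

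Protocol 4.2 presents acne and hirsutism as evidence of clinical benefit beyond biomarker control. SAP Section 4 makes the SAP govern where the two documents differ, so the protocol model cannot fill the gap. If the text stands, the programmer must choose the model when the data are in hand. For hirsutism, a fall of 1 point and a fall of 15 points would count alike.

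**Working it through.** **1. Can the referenced model be run?**

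| | Needed for 3.8 and 3.9 | 13.5.1.2 | 13.5.1.4 |
|---|---|---|---|
| Outcome | 3 ordered levels | A4 response, 0 or 1 | ordered A4 categories |
| Visits | Week 76 (also measured at Weeks 6 and 18) | Weeks 10, 14, 18 | Weeks 10, 14, 18 |
| Link | cumulative logit (Section 15) | logit | cumulative logit |
| Own baseline score | yes (Protocol 9.4.4.4) | no | no |
| Sex | constant for mFG | included | included |

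Section 13.5.1.2 fails on outcome, visits and link. Section 13.5.1.4 has the right link but the wrong visits. Both lack the baseline score.

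**2. Does another rule restore the baseline score?** SAP 10.1 adds the endpoint's own baseline for continuous endpoints. Section 15 classes IGA and mFG as ordinal and not continuous, so 10.1 does not reach them. Section 15 declares the change of model but not the loss of the covariate.

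**3. When does the collapse apply?** Avoiding it takes 5 distinct change values with 5 subjects each: 5 × 5 = 25 evaluable subjects at the very least. The plan's target reproduces: 15 / 0.85 = 17.6, so 18 per group and 4 × 18 = 72. After 15% dropout, 72 × 0.85 is about 61. If half are women (assumed), about 31 remain before requiring mFG ≥ 8. Below 25 the rule fires with certainty. Above that, 4,000 simulated trials per scenario (integer mFG change, assumed mean −1 or −3, SD 2, 4 or 6) gave:

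| Evaluable women | Rule fires |
|---|---|
| 30 | 99.5–100% |
| 36 | 91–100% |
| 45 | 53–100% |
| 61 (every remaining subject a hirsute woman) | 7–80% |

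A wider spread of change makes firing more likely at N = 30 to 45, so the rule bites hardest where the scale discriminates most.

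**4. What does the collapse cost in a treatment-group contrast?** Under proportional odds, information is proportional to 1 − Σp³ over the categories. Example for mFG, mean −2 and SD 4: the three-way split is 0.646 / 0.088 / 0.266, so 1 − (0.270 + 0.001 + 0.019) is about 0.711. Over all integer values it is 0.994. The ratio is 0.71.

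| Assumed mean change in mFG (SD 2 to 6) | Information kept |
|---|---|
| −1 | 79% |
| −2 | 55–75% |
| −3 | 29–69% |

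For IGA, on an assumed 0–4 scale with two assumed change distributions, the ratios are 0.836 / 0.906 = 92% and 0.840 / 0.939 = 89%.

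**5. What does it cost for the Week 76 versus baseline question?** Illustration with 18 women (assumed), mean −2 or −3, SD 4 or 4.5, two-sided 5%: using direction only, power is roughly 28% to 66%; a signed-rank test on the full change gives roughly 41% to 84%. The gap is 13 to 19 points in each scenario.

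**6. What does omitting the baseline score cost?** Taking the share kept as 1 − ρ², with ρ its correlation with change: a loss of 4%, 9%, 25% or 36% for ρ = 0.2, 0.3, 0.5 or 0.6. The documents give no value of ρ.

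**The case against.** The best defence is that the intention is clear. Section 13.5.7 calls the endpoints ordinal, Section 15 names the cumulative logit, and the example code in 13.5.1.2 even specifies a multinomial distribution. A reader might infer that the sponsor chose to dichotomise both scales; the documents do not support that. This is a cross-reference error. It still needs correcting: the text of 13.5.1.2 says binomial with a logit link, and 13.5.1.4 would also need new visits and covariates.

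The collapse can be defended as pre-specified and reasoned, since a many-level cumulative logit across four arms in some 18 women could be unstable. That holds against an uncollapsed cumulative logit, but not against the ANCOVA or rank-based ANCOVA that 13.5.7 already applies to SF-36 and TART volume. The wording is also unclear on whether the collapse always applies or only when the sparsity test is met.

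On the baseline score, the outcome is already a change, and every woman analysed starts at 8 or above and so has room to improve. That limits the loss; it does not explain an undeclared departure. Sex is absent from the example MODEL statement, but so are log baseline A4 and GC dose, which the text requires.

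Two further limits stand. The 0–36 range belongs to the score, not to its change. And a reader might want to express the loss as power for one arm against another. Protocol 9.4.1 and SAP 13.5.7 set the Week 76 question as change from baseline, and all subjects move to 200 mg at Week 30, so there is no concurrent placebo at that visit.

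**Conclusion.** The model reference is wrong and the baseline score has been dropped without declaration. Both follow from the text alone, for both scales.

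For hirsutism the collapse would almost certainly apply, and the loss is material: 21% to 71% of the information for assumed mean falls of 1 to 3 points. That range depends on the assumed distribution of change; the near-certainty of collapse depends on the assumed number of hirsute women. The documents give neither, so the figures are illustrative.

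A reader might infer that much of the information is lost for acne as well. The check does not support that: the loss is about 10% on an assumed 0–4 scale, so the acne point rests on the reference and the covariate.

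Both endpoints are exploratory, without alpha control under SAP 10.5. No primary or secondary conclusion is affected.

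**What to change.** - **IGA:** replace the reference to 13.5.1.2 with a cumulative logit of the 13.5.1.4 form, written out for the analysed visit.
- **Both scales:** include the scale's own baseline score. For mFG, drop sex.
- **mFG:** analyse the uncollapsed change. For any treatment-group contrast, use the baseline-adjusted ANCOVA already applied to 3.7 and 3.11, rank-based if residuals are non-normal. For Week 76 versus baseline, add a signed-rank test or an estimated mean change with its confidence interval. Rank ANCOVA alone cannot answer that question, because adding a constant to every change leaves the ranks as they were. Keep better / same / worse as a descriptive summary.
- **Section 15:** record these changes.

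The cost is SAP wording and programming. The baseline scores are already collected at Week 6, so no new data are needed.
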